12.8 Serious Adverse Event Reporting

12.8.1 Trial sites/investigators

All SAEs that occur from the time a patient has signed consent for the Trial to within 30 days of the final protocol-specified treatment are required to be reported to the Sponsor whether or not considered related to the treatment under investigation.

The Principal Investigator (PI) must:

- Determine whether an AE is 'Serious'
- For SAEs, the PI must then ascertain the suspected cause
- The attribution to the SAE must be recorded in the patients' medical records and reported on the SAE form.

SAEs must be reported by completing the SABRseq SAE form and emailing/faxing to the following:

Sponsor (or delegate)	[contact]
Merck Global Safety	[contact]
Merck Canada INC	[name] or [contact]

SAE forms are required at the following points:

Initial Report	Within one working day/24 hours of discovery or notification of the event. If the reporting of an SAE is delayed by more than 24 hours, an explanation must be provided on the SAE form.
Incomplete Reports	If all details are not available at the time of the initial report a completed report must be sent within the next 10 days.
Updated Report	If the event is not resolved (or 'on-going') at the time of the initial report, the SAE Form must be submitted every 30 days until the event is resolved, death has occurred or the condition has stabilised. If a change occurs in a stable condition (i.e. either worsens or improves), then a new SAE Form should be faxed

The Investigator is ultimately responsible for reporting the SAE and must sign the final SAE report(s). Should this Investigator not be available to sign the initial SAE form within the 24-hour period, a comment to this effect must be written on the form and the form signed by

the clinician attending to the patient at the time and faxed to the Sponsor. The investigator must sign the SAE form as soon as possible and re-fax to the Sponsor.

The Investigator at the Trial Site is responsible for determining the local SAE reporting requirements of the responsible HREC and subsequently notifying the HREC of SAEs as required.

All SAEs that have not resolved by the end of the study, or that have not resolved upon discontinuation of the patients participation in the study, must be followed until any of the following occurs:

- The event resolves
- The event stabilizes
- The event returns to baseline, if a baseline value/status is available
- The event can be attributed to agents other than the study drug or to factors unrelated to study conduct
- It becomes unlikely that any additional information can be obtained (patient or health care practitioner refusal to provide additional information, lost to follow-up after demonstration of due diligence with follow-up efforts)

12.8.2 Sponsor

The Sponsor is responsible for:

- Implementing and maintaining a suitable recording system to record information from all SAEs received from Trial Sites.
- Ensuring that the Coordinating Principal Investigator (CPI) is notified of each SAE to enable the SAE to be assessed by the CPI and any other appropriate reviewers for nature (expected/unexpected), causality and whether the appropriate regulatory authority need to be notified of the SAE.
- Notifying the appropriate regulatory authority in accordance with the regulatory authority's detailed guidance of any SUSARs that are fatal or life threatening as soon as possible but no later than 7 days after the site gained first knowledge of the event. Incomplete reports must be completed and forwarded as soon as possible within 8 additional calendar days. All other serious, unexpected ADRs should be reported to the TGA within 15 days after the site gained first knowledge of the event.
- Considering information provided by (non-serious) adverse event data.
- Informing each trial site of new information arising from serious and non-serious adverse events and adverse drug reactions that may affect the conduct of the Trial, or the rights, interests, safety or wellbeing of trial patients.
- Notifying the appropriate regulatory authority of any significant issue that has arisen from analysis of overseas reports or action that has been taken by another country's regulatory authority within 72 hours of first knowledge.

12.9 Events of Clinical Interest

Selected non-serious and serious adverse events are also known as Events of Clinical Interest (ECI) and must be recorded as such on the Adverse Event case report forms and reported within 24 hours to the Sponsor and within 2 working days to Merck Global Safety. (Attn: Worldwide Product Safety; [contact]).

For the time period beginning at first treatment through 90 days following cessation of treatment, or 30 days following cessation of treatment if the patient initiates new anticancer therapy, whichever is earlier, any ECI, or follow up to an ECI, whether or not related to protocol treatment, must be reported within 24 hours to the Sponsor and within 24 hours to Merck Global Safety.

Events of clinical interest for this trial include:

1. an overdose of pembrolizumab, as defined in Section 12.10 Definition of an Overdose for This Protocol and Reporting of Overdose to the Sponsor, that is not associated with clinical symptoms or abnormal laboratory results.
2. an elevated AST or ALT lab value that is greater than or equal to 3X the upper limit of normal and an elevated total bilirubin lab value that is greater than or equal to 2X the upper limit of normal and, at the same time, an alkaline phosphatase lab value that is less than 2X the upper limit of normal, as determined by way of protocol-specified laboratory testing or unscheduled laboratory testing.

12.10 Overdose Definition and Reporting

For purposes of this trial, an overdose of pembrolizumab will be defined as any dose of 1,000 mg or greater (≥ 5 times the indicated dose). No specific information is available on the treatment of overdose of pembrolizumab. Appropriate supportive treatment should be provided if clinically indicated. In the event of overdose, the patient should be observed closely for signs of toxicity. Appropriate supportive treatment should be provided if clinically indicated.

If an adverse event(s) is associated with (“results from”) the overdose of pembrolizumab, the adverse event(s) is reported as a serious adverse event, even if no other seriousness criteria are met.

If a dose of pembrolizumab meeting the protocol definition of overdose is taken without any associated clinical symptoms or abnormal laboratory results, the overdose is reported as a non-serious Event of Clinical Interest (ECI), using the terminology “accidental or intentional overdose without adverse effect” on the relevant Adverse Event eCRF.

All reports of overdose with and without an adverse event must be reported within 24 hours to the Sponsor and within 2 working days hours to Merck Global Safety. (Attn: Worldwide Product Safety; [contact]).

12.11 Reporting of Pregnancy and Lactation to the Sponsor and to Merck

Although pregnancy and lactation are not considered adverse events, it is the responsibility of investigators or their designees to report any pregnancy or lactation in a patient (spontaneously reported to them), including the pregnancy of a male patient's female partner that occurs during the trial or within 120 days of completing the trial completing the trial, or 30 days following cessation of treatment if the patient initiates new anticancer therapy, whichever is earlier. All patients and female partners of male patients who become pregnant must be followed to the completion/termination of the pregnancy. Pregnancy outcomes of spontaneous abortion, missed abortion, benign hydatidiform mole, blighted ovum, fetal death, intrauterine death, miscarriage and stillbirth must be reported as serious events (Important Medical Events). If the pregnancy continues to term, the outcome (health of infant) must also be reported.

Such events must be reported within 24 hours to the Sponsor and within 2 working days to Merck Global Safety. (Attn: Worldwide Product Safety; [contact])

13. Response Assessment

Response and progression will be evaluated in this study using RECIST 1.1, irRECIST, Peter Mac Metabolic Response Criteria and PERCIST 1.0.

13.1 Evaluation of response by RECIST1.1 and irRECIST

The same imaging modality as used at screening (i.e. CT or MRI scans) should be used at every visit. Changes only in the largest diameter (unidirectional measurement) of the tumour lesions are used in the RECIST v1.1 criteria. For tumour lymph nodes, the short axis must be measured. Lesions are measurable or non-measurable using the definitions described below. Refer to Appendix 3 and 4.

13.2 Peter Mac Metabolic Response Criteria

Metabolic response in a lesion will be assessed according to the method given in MacManus et al. Scans are read visually displayed side by side with liver uptake normalised between images. Response categories are defined as follows (comparison is with baseline PET scans in each case):

- **Complete metabolic response (CMR_V):** Activity within the tumour site has decreased to be equal to or less than adjacent soft tissue in the radiation treatment volume.
- **Partial metabolic response (PMR_V):** Any appreciable reduction in intensity of tumour FDG uptake or in tumour volume.
- **Stable metabolic disease (SMD_V):** No appreciable change in intensity of tumour FDG uptake or in tumour volume.
- **Progressive metabolic disease (PMD_V):** Appreciable increase in tumour FDG uptake or in tumour volume.

13.3 PERCIST 1.0 Criteria

A region of interest (ROI) is used to assess the maximum SUL peak. This ROI is typically the region of the baseline tumour with the highest uptake, but it can also be another lesion that was previously present and is the most active lesion after treatment.

- **Complete metabolic response (CMR):** complete resolution of ^{18}F -FDG uptake within the measurable target lesion so that it is less than mean liver activity and indistinguishable from surrounding background blood-pool levels. Disappearance of all other lesions to background blood-pool level.
- **Partial metabolic response (PMR):** reduction greater or equal to 30% in the target measurable tumour ^{18}F -FDG SUL peak.
- **Stable metabolic disease (SMD):** disease other than CMR, PMR or PMD.
- **Progressive metabolic disease (PMD):** Greater than 30% increase in ^{18}F -FDG SUL peak OR visible increase in extent of ^{18}F -FDG tumour uptake (75% of total lesion glycolysis volume with no decline in SUL OR the advent of new ^{18}F -FDG-avid lesions that are typical of cancer and not related to treatment effect or infection.

14. Statistical Considerations

14.1 Statistical Analysis Plan Summary

This is a prospective, two-arm randomised, open label, Phase Ib study assessing safety, efficacy and biological effects of two different treatment sequences of the combination of SABR with pembrolizumab in patients with metastatic NSCLC.

14.2 Treatment Assignment

Patients will be randomised in the ratio of 1:1 between the two arms. Once randomisation is assigned, cancellation will not be permitted. Patients will be stratified by number of metastases to be treated with SABR (two groups: 1 metastasis vs 2 or 3 metastases), and by line of therapy (two groups: previously treated vs previously untreated).

14.3 Populations for Analyses

- Treated patient population is defined as the patients who completed at least one SABR treatment and received at least one dose of pembrolizumab. This is the primary population for the safety and efficacy analyses.
- Response-evaluable patients are those treated patients who have CT or PET scans performed at respective follow-up visit. This is the analysis population for the response endpoint.

Patients that are not part of the treated population will be replaced and no follow-up information will be collected.

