8.5 Follow-Up – All Arms

Patients who complete the treatment phase, or discontinue trial treatment for a reason other than disease progression will move into the follow-up phase. The following assessments will be performed every 3 months up until the last patient has completed 24 months of follow-up, until the start of new anti-neoplastic therapy, disease progression, death or end of the study.

- Physical examination
- Vital signs and weight
- Documentation of ECOG performance status
- Laboratory studies including FBE, biochemistry and coagulation, hepatic and kidney function tests (only if clinically indicated)
- Radiological evaluation with a CT Chest/Abdomen and Pelvis or MRI
- Whole body bone scan (only if clinical indicated)
- Response assessment
- Adverse Event assessment
- Blood samples for correlative studies
- New anti-cancer therapy status
- Fresh biopsy sample 3 months after the last dose of SABR if considered safe

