8.6 Survival Follow-up

Patients who discontinue trial treatment due to progression, progress during follow-up or commence a new systemic treatment will be followed for survival only. Survival status will be assessed every 3 months until death, withdrawal of consent, or the end of the study, whichever occurs first. Where possible, every effort should be made to record results of subsequent tumour assessments and any new anti-cancer therapies.

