14.4 Statistical Methods

Demographics and baseline characteristics of patients will be summarized using descriptive statistics. No imputation for missing values is intended. All statistical tests comparing the two arms will be 2-sided, 5% alpha will be used and no adjustment for multiplicity is intended.

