14.7 Response Analysis

All tumour response measurements (pre- and post-treatment) must be recorded using the definitions of RECIST 1.1. RECIST assessments will take into account post-treatment inflammatory processes that occur after SABR treatment in pulmonary and liver tissues. PET response criteria will also be assessed and reported. If a criterion is met in more than one response type then the response type will be classified at the lowest possible level. The initial assessment of response will be determined after all protocol treatment has been completed, whether or not all of the planned treatment was received. In addition, irRECIST, PERCIST and Peter Mac Metabolic Response criteria will be considered in conjunction to RECIST 1.1. Metabolic response criteria and PERCIST 1.0 results or assessments will not be entered by site clinical staff and will be reported centrally. Overall patient's response rates

(CR+PR at all lesions) at 6 and 12 months after commencement of SABR treatment will be described as percentages with exact 95% confidence interval. Overall response for all irradiated lesions and un-irradiated lesions will also be assessed separately. Lesion size of measurable lesions may be plotted over time to describe patient response trajectories. Overall response rates will be compared between treatment arms using Fisher's exact test.

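### Response at 6 and 12 months is calculated only on treated patients scanned at that visit, so deaths and unscanned progressors leave the denominator and overall response is biased upward

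*Combined protocol and SAP*

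**What the plan says.** Section 14.3 defines the treated population as patients with at least one SABR treatment and at least one pembrolizumab dose, and adds: "This is the primary population for the safety and efficacy analyses". It then sets a narrower population for response: "Response-evaluable patients are those treated patients who have CT or PET scans performed at respective follow-up visit".

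Section 14.7 gives the summary measure as "CR+PR at all lesions) at 6 and 12 months after commencement of SABR treatment will be described as percentages with exact 95% confidence interval", with Fisher's exact test between arms. It adds: "Overall response for all irradiated lesions and un-irradiated lesions will also be assessed separately". Section 14.4 states: "No imputation for missing values is intended". Table 10 in section 14.9 shows response precision with 16 patients per arm.

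Three places decide who still has a scheduled scan:

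- Section 8.6: "Patients who discontinue trial treatment due to progression, progress during follow-up or commence a new systemic treatment will be followed for survival only".
- Section 8.5 runs the 3-monthly follow-up assessments, imaging included, "until the start of new anti-neoplastic therapy, disease progression, death or end of the study".
- Footnote 10 to Tables 1 and 2 likewise ends follow-up imaging at progression.

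Two provisions work the other way. Footnote 1 and section 8.6 ask sites to try to record tumour assessments made after progression. Section 10.2 lets pembrolizumab continue after radiological progression at the investigator's discretion.

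**The concern.** A patient who has died by month 6 or 12 has no scan at that visit and so is not response-evaluable. A patient who stopped treatment for progression, progressed in follow-up or began new systemic therapy has no scheduled scan and is evaluable only if one happens to be done. Most of these patients leave because treatment failed. No section counts death, progression or a missing scan as non-response.

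The reported percentage is then the response rate among those still alive and still scanned, which is a different quantity from the rate among treated patients. The gap widens from 6 to 12 months as more patients leave. Section 4.13 expects the findings to serve as the basis for larger randomised studies, and an inflated response rate would carry into that planning.

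**Working it through.** **Inputs.** 16 treated patients per arm (14.9). 6-month overall survival of 80.2% in the pembrolizumab group of the cited first-line trial (4.12). As a less favourable alternative, median overall survival of 12.0 months for all patients in the cited phase I study (4.12). Median PFS of 10.3 months from the same first-line trial (4.12).

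**Assumptions.** Constant hazards; time from SABR taken as equal to time from randomisation; every responder scanned; responder counts of 6 at 6 months and 3 at 12 months chosen only for illustration.

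**1. The plan's own figures.** Exact (Clopper-Pearson) 95% intervals on n = 16 reproduce Table 10 after rounding: 6/16 gives 15.2 to 64.6; 8/16 gives 24.7 to 75.3; 10/16 gives 35.4 to 84.8; 12/16 gives 47.6 to 92.7. The table is right for a denominator of 16. The 14.3 rule gives 16 only if every treated patient is scanned at the visit.

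**2. Formula.** With x responders, all scanned, and m treated patients without a scan, the plan reports x/(16 − m). The all-treated rate is x/16. The inflation factor is 16/(16 − m).

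**3. Deaths only, 6-month survival 80.2%.**

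- Alive at 6 months: 16 × 0.802 = 12.8, about 13.
- Alive at 12 months: 16 × 0.802² = 10.3, about 10.

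| Visit | All treated (95% CI) | As planned (95% CI) | Factor |
|---|---|---|---|
| 6 months | 6/16 = 37.5% (15 to 65) | 6/13 = 46% (19 to 75) | 16/13 = 1.23 |
| 12 months | 3/16 = 19% (4 to 46) | 3/10 = 30% (7 to 65) | 16/10 = 1.6 |

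**4. Deaths only, median survival 12.0 months.** Alive: 16 × 0.5^(6/12) = 11.3, about 11, and 16 × 0.5 = 8. The reported rates become 6/11 = 55% (23 to 83) and 3/8 = 38% (9 to 76).

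**5. Progressors.** With median PFS 10.3 months, the number progressed or dead is 16 × (1 − 0.5^(6/10.3)) = 5.3 at 6 months and 16 × (1 − 0.5^(12/10.3)) = 8.9 at 12 months. If none of the living progressors were scanned, the denominators would be about 11 and 7, giving 6/11 = 55% and 3/7 = 43%. For that PFS assumption this is the outer limit of loss through progression or death, because some progressors will still be scanned. The documents do not say how many, so the true figure lies somewhere between steps 3 and 5 if the first-line trial's survival and PFS apply.

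**The case against.** The best defence is that the loss is partial. Progressors may stay on pembrolizumab and keep their treatment-phase scans, and sites are asked to record later assessments. That stands, and it is why the effect of progressors cannot be given as one number. It does not remove the bias: both routes are discretionary, and neither recovers a death.

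The no-imputation sentence follows one on baseline characteristics and might be meant only for them. Even so, no other section supplies a non-response rule.

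The consequence is also limited. Response is a secondary endpoint in a 32-patient Phase Ib trial, the population is openly labelled, and PFS, OS and the event-history chart (14.6) show who progressed or died. That makes the problem visible but leaves the reported rate as it is.

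The survival inputs come from pembrolizumab alone in selected patients. This trial also admits previously treated patients, for whom 4.12 cites median PFS of 3.0 and 3.9 months. The figures illustrate the mechanism and do not forecast this trial.

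A reader might infer more than the documents support:

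- **That irradiated-lesion response is also inflated.** A patient who leaves because of a new or non-irradiated lesion may still have responding irradiated lesions, so the direction is open.
- **That the rule favours one arm.** Section 8.3.3 makes Arm 2 CT and response assessment conditional on clinical indication, while 8.2.3, Table 2 and footnote 10 do not. If scans were conditional, deteriorating patients might be scanned more and well responders less, which could lower the Arm 2 rate. Neither the direction nor the size of any difference follows.
- **That PET response is planned at 6 and 12 months without scans.** Those rates are stated as CR+PR, whereas section 13 gives the PET criteria in metabolic categories. The PET analysis in 14.9 comes after 5 cycles, close to the one scheduled post-baseline PET.

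**Conclusion.** The concern holds for overall response at 6 and 12 months. Relative to the treated population, the planned rate is biased upward, because patients who have died, and progressors who are no longer scanned, are removed when they should count as non-responders. Under RECIST 1.1 this is clear for both groups. Under irRECIST it is clear for deaths, but an unconfirmed progressor could later respond.

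From deaths alone, the rate is multiplied by about 1.2 at 6 months and 1.6 at 12 months under the first-line survival figure, and by about 1.5 (16/11) and 2 (16/8) under the 12.0-month median. Unscanned progressors raise it further by an unknown amount. These sizes rest on constant hazards, external survival figures and every responder being scanned. A responder who misses a scan would pull the scanned-only rate the other way.

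The upward direction is not established for irradiated lesions alone, and no direction is established for the difference between arms. The toxicity analysis and the sample size are unaffected.

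**What to change.** In 14.3 and 14.7, make all treated patients the denominator for 6- and 12-month overall and non-irradiated response, and for the Fisher comparison. Count as non-response:

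- death before the visit;
- start of new systemic therapy before the visit;
- no assessment at the visit;
- earlier progression by the same criterion and lesion set. For RECIST 1.1 this is RECIST progression. For irRECIST it is confirmed irPD only, and otherwise the status at the visit applies, because Appendix 4 recommends confirmation and 10.2 allows treatment past radiological progression.

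Report the scanned-only rate and the number scanned per arm as supportive. For irradiated lesions, report both rates, with the all-treated rate labelled as a lower bound.

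Separately, reconcile 8.3.3 with 8.2.3, Table 2 and footnote 10 on whether Arm 2 CT and response assessment are conditional, since conditional scanning in one arm would make the scanned group differ by arm.

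**Cost.** The denominator change is a wording amendment to section 14 and needs no new data. Reported rates will be lower, and a responder who misses a scan counts as a non-responder, which the supportive rate makes visible. Reconciling 8.3.3 cannot recover Arm 2 scans already omitted, if any were.

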Eligible patients will be randomised to either:

Arm 1: SABR followed by pembrolizumab; *or*

Arm 2: Pembrolizumab followed by SABR after cycle 1

Refer to Trial Schema

Pembrolizumab at a dose of 200 mg will be delivered every 3 weeks for a total duration of 102 weeks (34 cycles), commencing either 7 days (+/- 2 days) before the first dose of SABR or 7 days (+/-2 days) after the last dose of SABR.

Tumour response will be assessed according to RECIST 1.1, and irRECIST, Peter Mac Metabolic Response Criteria and PERCIST 1.0. Responses will be characterized in lesions treated with SABR and in un-irradiated lesions.

Peripheral blood samples and where possible, tumour tissue will be collected pre, during and post-treatment to assess baseline findings and longitudinal changes in immune subsets within tumour tissue and peripheral blood.

Evaluable patients are those that receive at least one dose of pembrolizumab and one dose of SABR. Non-evaluable patients will be replaced until the planned sample size has been reached.

7. Study Population

Patients with metastatic NSCLC who meet the inclusion/exclusion criteria described below will be eligible for participation in this study.

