7.6 Patient Treatment Withdrawal/Discontinuation

Patients may withdraw consent at any time for any reason or be withdrawn from the trial treatment at the discretion of the investigator should any untoward effect occur. In addition, a patient may be withdrawn by the investigator or the Sponsor if continued enrolment into the trial is inappropriate for administrative and/or other safety reasons.

A trial patient may discontinue trial treatment for any of the following reasons:

- Disease progression
- Unacceptable adverse event
- Intercurrent illness which prevents further treatment
- Withdrawal of consent for treatment or from trial by the patient
- The investigator believes it is in the best interest of the patient
- The patient becomes pregnant or begins breastfeeding
- Noncompliance with the protocol

When a patient discontinues/withdraws prior to completion of protocol treatment, patients should attend the site for a 30-day (post end of trial treatment) safety follow-up visit for assessment of AEs and efficacy. Any AEs which are present at the time of

discontinuation/withdrawal should be followed in accordance with the safety requirements. The reason for discontinuation will be recorded on a CRF.

Discontinuation of trial treatment does not necessarily indicate withdrawal from the trial. Patients are expected to have follow-up assessments after treatment discontinuation if patients' agree and reason for trial treatment discontinuation permits.

Total withdrawal would occur in the circumstance that the patient decides to completely withdraw from all treatment aspects of the trial, and does not agree to any further scheduled follow up assessments. The patients' total withdrawal must be documented in the medical records and transcribed onto the relevant CRF. No further information will be collected from this patient for the purpose of this trial.

8. Study Assessments

The following assessments will occur during the trial. A schedule of assessments is provided on page 11.

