12.6 Adverse Events Reporting

All adverse events, which occur whilst the patient is enrolled on the trial, must be reported in the patients' medical records and recorded on the relevant CRF.

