14.5 Safety Analysis

Safety will be assessed using CTCAE v4.03 and the maximum toxicity grade per patient of each adverse event will be derived and presented in table format according to arm and overall. The number of patients who suffer from grade 3 or higher toxicities (for each toxicity type and overall) will be provided considering all patients who have received at least one dose of pembrolizumab and completed at least one SABR treatment. The safety analysis will be conducted twice: once for all AE's, regardless of relatedness to treatment and once considering only AE's related to the treatment (i.e. classified as possibly, probably or definitely related).

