14.10 Early Termination Criteria

Consideration of suspension of patient accrual will occur if an unacceptable rate of toxicity is detected. The expected rates of grade 3+ pneumonitis and colitis are expected to be less than 5%. If at any given time during the trial 3 or more patients present with treatment related pneumonitis or colitis of grade 3-4 toxicity, data will be reviewed by the TMC and consideration will be given to permanently suspend recruitment and close the trial

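### The primary safety and efficacy sets require receipt of both SABR and pembrolizumab, so toxicity or death that prevents the second modality drops out of the primary analyses

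*Combined protocol and SAP*

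**What the plan says.** Section 14.3: "Treated patient population is defined as the patients who completed at least one SABR treatment and received at least one dose of pembrolizumab". The section names this set as primary for both safety and efficacy. Section 14.5 uses the same denominator for the grade 3 or higher counts, "considering all patients who have received at least one dose of pembrolizumab and completed at least one SABR treatment".

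Patients outside the set are replaced. Section 6 says "Non-evaluable patients will be replaced until the planned sample size has been reached", and section 14.3 goes further: "Patients that are not part of the treated population will be replaced and no follow-up information will be collected". The only other set defined, for response, is a subset of the treated patients.

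Other sections treat patients who stop early differently:

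- Section 7.6: those who stop before completing treatment still have a visit: "patients should attend the site for a 30-day (post end of trial treatment) safety follow-up visit for assessment of AEs and efficacy".
- Section 12.6: "All adverse events, which occur whilst the patient is enrolled on the trial, must be reported".
- Section 12.8.1 requires reporting of "All SAEs that occur from the time a patient has signed consent for the Trial to within 30 days of the final protocol-specified treatment".
- Sections 8.5 and 8.6 send patients who stop treatment into the follow-up phase or into survival follow-up, depending on the reason.
- The review trigger in section 14.10 is not limited to the treated set: "If at any given time during the trial 3 or more patients present with treatment related pneumonitis or colitis".

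Section 5.3 times PFS and OS from randomisation. Section 7.3 does not allow a randomisation to be cancelled.

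**The concern.** The primary objective is the toxicity of the combination when SABR comes before or after the first pembrolizumab cycle. Harm severe enough to break the sequence is part of the answer, yet the primary table leaves it out. The omission also depends on arm. Arm 1 can lose patients harmed by SABR before any pembrolizumab, and Arm 2 can lose patients harmed by the first pembrolizumab dose before SABR. Tables set side by side by arm would then leave out different kinds of event.

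For PFS and OS, membership of the analysis set is decided after the clock has started. A death before the second modality cannot count as an event, so the comparison is not made in all randomised patients.

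The no-follow-up clause makes this permanent, because survival and later adverse event data that are never collected cannot be recovered for a sensitivity analysis.

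**Working it through.** **1. Route to exclusion.** Section 7.6 lists an unacceptable adverse event, intercurrent illness and progression among the reasons for stopping trial treatment. Any of these, or death, can fall between the two modalities. Table 5 in section 8.8 may be a further route. It ends further trial treatment after a severe infusion reaction, and in Arm 2 the first infusion precedes SABR. Whether that phrase covers SABR is not clear.

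**2. Time at risk.** Section 10 sets the gap at 7 ± 2 days, that is 5 to 9 days. Section 9.1 lets SABR to several lesions span 7 calendar days, so in Arm 1 the time from first SABR to first pembrolizumab can reach 6 + 9 = 15 days. Section 9.3 allows 28 days from randomisation to first treatment. By these windows, a patient may have to survive up to 28 + 6 + 9 = 43 days in Arm 1, or 28 + 9 = 37 days in Arm 2, to enter the PFS and OS analysis.

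**3. The plan's own figure.** Table 9 uses 1 − (1 − p)^n. With p = 0.10 and n = 16 this is 1 − 0.9^16 = 0.815, as stated. All eight entries of the table reproduce. Sixteen is the smallest n that reaches 80% at a 10% rate.

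**4. One excluded patient.** Suppose one patient in an arm has a grade 3 or higher event after the first modality, never receives the second and is replaced, and none of the 16 fully treated patients has that event.

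| Set | Count | Rate | Exact 95% CI |
|---|---|---|---|
| Any treatment received | 1/17 | 5.9% | 0.1 to 28.7% |
| Both modalities received | 0/16 | 0% | 0 to 20.6% |

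**5. Effect on detection.** Let f be the share of patients with a given toxicity who are excluded and replaced because of it. The documents give no value for f, so a range is assumed. The rate visible in the treated set is q = p(1 − f)/(1 − pf), and the chance of at least one case among 16 is 1 − (1 − q)^16. With p = 0.10:

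| f (assumed) | q | Chance of at least one case |
|---|---|---|
| 0 | 0.1000 | 0.815 |
| 10% | 0.0909 | 0.782 |
| 20% | 0.0816 | 0.744 |
| 25% | 0.0769 | 0.722 |

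The 80% target is just met when q = 1 − 0.2^(1/16) = 0.0957. That gives f = (0.10 − 0.0957)/(0.10 × (1 − 0.0957)) = 0.048, or about 5%.

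**6. The follow-up clause against the rest of the protocol.** Tables 1 and 2 place the 30-day safety visit in the follow-up phase. Even if the clause refers only to that phase, it contradicts section 7.6, and it contradicts sections 8.5 and 8.6 directly. If it is read more broadly, it also conflicts with sections 12.6 and 12.8.1. On either reading, survival and later adverse events are lost.

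**The case against.** Requiring exposure to both modalities is a recognisable Phase Ib choice, since the endpoint and Table 9 are framed around the combination. A delay does not exclude anyone: section 14.3 asks only for at least one of each modality, so only patients who never receive the second are lost.

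The Table 5 route is doubtful. The table concerns pembrolizumab infusions, and section 10 uses the term trial treatment for the Day 1 dose. Section 4.12 reports that one infusion reaction led to discontinuation among 495 patients. Carried over to 16 Arm 2 patients, that is 16/495 = 0.03 expected events, although those patients had other doses and no SABR. Much pembrolizumab toxicity will arise well after the short gap. Section 14.5 plans no between-arm test of toxicity, the two intervals in step 4 overlap heavily, and excluded events still reach the sponsor.

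Most of this stands as a limit on size. Exclusions should be few, f is hypothetical, and the 5% break-even partly reflects the thin margin of 0.815 over 0.80. It does not answer the point itself. Section 7.6 provides routes that do not depend on Table 5, no supplementary set is defined, and an event known to the sponsor is still absent from the primary table. The both-modalities set is reasonable as a description of patients who completed the sequence, but not as the only basis for the safety result.

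**Conclusion.** The concern holds and should be fixed. The population and replacement rules are explicit, and the omission of sequence-breaking events from the primary tables follows directly from them. The expected number of exclusions is small but unknown. One exclusion in an arm is enough to move a reported rate from 5.9% to 0%, and a loss of about 5% of patients with a 10% toxicity takes detection below the design target. That second figure rests on an assumed f; the first is a worked example with one event. Table 9 itself is arithmetically correct; the weakness lies in the population it is applied to. For PFS and OS, which are secondary, the analysis is still by arm but is conditioned on an event after randomisation. Safety oversight is not compromised, because adverse event recording, SAE reporting and the review trigger are not restricted to this set.

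**What to change.** - In sections 14.3 and 14.5, define the safety population as all randomised patients who received any SABR or any pembrolizumab, tabulated by arm.
- Analyse PFS and OS in all randomised patients.
- Keep the both-modalities set as a supportive analysis for safety and efficacy.
- Delete the clause in section 14.3 that stops follow-up. Follow these patients for survival and, if they received any treatment, for adverse events. Reconcile sections 6, 14.3 and 14.5 with sections 7.6, 8.5, 8.6, 12.6 and 12.8.1.
- Replacement up to 16 fully treated patients per arm can stay, with the number replaced and the reasons reported by arm.
- State whether the discontinuation wording in Table 5 refers to pembrolizumab alone or also to SABR, so that membership of each set is unambiguous.

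The cost is a few wording changes and the follow-up of a small number of extra patients whose adverse events are already reportable. The safety denominator may exceed 16 per arm, and reported toxicity may be slightly higher. Detection does not suffer: at a true rate of 10% it stays at 0.815 with 16 patients and becomes 1 − 0.9^17 = 0.833 with 17 or 1 − 0.9^18 = 0.850 with 18.
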